##### **Abnormality analysis**

For all parameters, an “on-treatment” analysis will be performed using all post-baseline assessments done during the on-treatment period, including rechecked values. Counts of patients with post-baseline PCSAs will be provided in summary tables regardless of the normal or abnormal status of the baseline by age group.

## **Descriptive statistics**

For heart rate (in beats/minute) and blood pressure (in mmHg) observed raw data and change from baseline will be summarized in descriptive statistics, for each type of measurement, parameter and time point.

## **Listings**

All individual data, including rechecked values, will be listed by type of measurement. In the listings, values will be flagged when reaching the limits of the PCSA criteria, when defined. A data listing of individual post-baseline abnormalities by patient will be provided.

Comments related to vital sign evaluations will also be listed, if any.

### **11.4.2.4 *Electrocardiogram***

Heart rate (in bpm), PR (in ms), QRS (in ms), QT-intervals (in ms) and corrected QT-intervals (QTc) will be analyzed as raw parameter values and change from baseline (for HR, PR, QT, QTc). Outlier summaries for the ECG parameters (eg, QTc) will also be created.

The values to be used as the baselines will be the mean of the triplicate measurements on Day 1/Week 0 pre-IMP values. If any of the scheduled baseline tests are repeated for any patient, the last rechecked values will be considered as baselines, provided they were done prior to the first olipudase alfa infusion.

## **Abnormality analysis**

For all parameters, an “on-treatment” analysis will be performed using all post-baseline assessments done during the on-treatment period, including rechecked values. Counts of patients with post-baseline PCSAs will be provided in summary tables regardless of the normal or abnormal status of the baseline by age group.

## **Descriptive statistics**

For all parameters, raw data and changes from baseline will be summarized in descriptive statistics for each time point.

## **Listings**

All individual data, including rechecked values, will be listed by type of measurement. In the listings, values will be flagged when reaching the limits of the PCSA criteria, when defined. A data listing of individual post-baseline abnormalities by patient will be provided.

Comments related to vital sign evaluations will also be listed, if any.

#### **11.4.2.5 Physical examinations and neurological examinations**

The frequencies and percent of patients with normal/abnormal findings at baseline and successive visits will be summarized.

#### **11.4.2.6 Echocardiogram and liver ultrasound Doppler**

Echocardiogram and liver ultrasound Doppler data will be presented for appropriate visits using raw data in listings and/or by descriptive statistics. Likewise, categorical data will be summarized using frequencies and percents at appropriate visits.

#### **11.4.2.7 Safety biomarkers**

For safety biomarkers of ceramide, cardiac troponin I, hsCRP, calcitonin, iron, ferritin, IL-6 and IL-8 raw values and change from baseline will be summarized using descriptive statistics by age group cohort, time point, highest tolerated dose and overall time point.

#### **11.4.2.8 Anti-olipudase alfa IgG antibodies, neutralizing antibodies, and other immune response assessments**

Percentage of patients who seroconverted to olipudase alfa, time to seroconversion and peak IgG antibody titer will be summarized using descriptive statistics. IgG antibody titer values will be summarized using descriptive statistics at each study visit. All data will be presented in listings for each patient.

By patient listings will also display results of neutralizing antibody, circulating immune complex, anti-olipudase alfa IgE antibody, serum tryptase activity, complement activation, and skin testing performed. Descriptive summaries may also be provided as appropriate.

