Clinical chemistry g , hematology g , coagulation g , urinalysis g	X	X		X		X				X	X	X											
$\beta$ -hCG pregnancy test i	X	X	Every 4 weeks from Day 1: Wk4, Wk8, Wk12, Wk16, Wk20, Wk24, Wk28, Wk32, Wk36, Wk40, Wk44, Wk48, Wk 52, Wk 56, Wk 60, Wk 64								X												
Safety biomarkers g		X	X	X	X	X	X			X	X	X	X										
Anti-olipudase alfa IgG and neutralizing antibodies in IgG positive patients		X	Every 2 weeks from Day 1 through Wk16, then at quarterly visits (Wk26, Wk38, Wk52) and Wk 64										X										
Anti-olipudase alfa IgE antibody test		In the event of a moderate/severe or recurrent-infusion associated reaction suggestive of hypersensitivity, a sample will be collected $\geq$ 3 days after event or prior to next infusion.																					
Serum tryptase and complement activation		In the event of a moderate/severe or recurrent-infusion associated reaction suggestive of hypersensitivity, a sample will be collected within 1 to 3 hours of event onset.																					
Skin testing		As necessary for assessing hypersensitivity reactions. See study manual.																					
Exploratory efficacy																							
Spleen volume by abdominal	X						X				X		X e										

DAY/WEEK (Wk)	Screening		Treatment Period a, b									Post-treatment Observations	
	Day -60 to Day -1	Day1 /Wk0	Wk 2 to Wk 10	W12 QV	Wk 14 to Wk 24	Wk 26 QV	Wk 28 to Wk 36 c	Wk 40 to Wk 50, Wk 54 to WK 62	Wk 38 QV	Wk 52 QV	Wk 64	Withdrawal	Follow-up
MRIj													
Liver volume by abdominal MRI j	X						X			X		X e	
Pulmonary imaging with HRCT	X									X		X e	
Pulmonary function test k	X						X			X		X e	
Chest X-ray l	X									X		X e	
Bone age by hand X-ray	X									X		X e	
Cycle ergometry m	X						X			X		X e	
Physician's global assessment	X						X			X		X	
Efficacy biomarkers		X					X			X	X	X	
Lipid profile	X	X n		X n			X			X	X	X	
Serum bone-specific ALP and C-telopeptide n		X					X			X	X	X	
Health outcome questionnaires	X						X			X		X e	
Cognitive and adaptive function testing o	X						X			X		X e	
Pharmacodynamics													
Plasma and/or DBS sphingomyelin and metabolite concentrations g			X	X	X	X	X			X	X	X	X

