2.6.11 Immune response assessments

An immune reaction against an exogenously administered recombinant protein plays a critical role in the safety of such compounds. Therefore, safety assessments will also include blood samples for anti-olipudase alfa immunoglobulin G (IgG) antibodies and neutralizing antibody formation in patients testing positive for ADA when appropriate.

In the event that a patient experiences a moderate, severe, or recurrent IAR suggestive of hypersensitivity reactions, additional blood samples will be collected for the evaluation of:

- Circulating immune complex detection; and,
- Immunoglobulin E (IgE) ADA, serum tryptase, and complement activation.

Additionally, skin testing may be performed, as appropriate, in patients who experience an IAR that meets the following criteria:

- IAR is suggestive of IgE ADA – mediated hypersensitivity reaction, with persistent symptoms of bronchospasm, hypotension and/or urticaria requiring intervention,
- Or any other signs or symptoms at the discretion of the investigator or the sponsor.

For ADA summaries, the baseline is the last non-missing ADA assessment prior to the first IMP.

Data listings will be provided to display results of anti-olipudase IgG antibody, neutralizing antibody, anti-olipudase alfa IgE antibody, serum tryptase activity, complement activation, and skin testing performed. If IgG ADA titer value is reported as <xx, the numeric value will be imputed as xx, the minimum required dilution (MRD), and used for summary purposes. Listing will provide results as reported as well as results as imputed.

A patient with at least one anti-drug antibody (ADA) response available in the database is considered evaluable.

A patient whose ADA status is positive at baseline is considered to have pre-existing ADA.

A patient whose ADA status is positive anytime post-baseline and is negative or missing at baseline is considered to have treatment-induced ADA.

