ADA Incidence = $100 * (\text{treatment-boosted} + \text{treatment-induced ADA positive patients}) / \text{number of evaluable patients}$.

The following information will be provided by age group cohorts and overall:

- Number of ADA evaluable patients
- Number (%) of patients with ADA positive/negative at baseline
- Number (%) of patients that never develop ADA at any time (i.e, ADA always negative during baseline and post-baseline)
- Number (%) of patients with treatment-boosted ADA
- Number (%) of patients with treatment-induced ADA
- Treatment emergent ADA: Number (%) of patients with treatment-boosted/treatment-induced ADA
- Duration of ADA response: Number (%) of patients with transient/persistent/indeterminate ADA response (each category separately)
- Number (%) of patients within persistent ADA response sub-classifications: low response, intermediate response, tolerized (each category separately)
- Patients with treatment induced ADA will be further characterized
 - Peak ADA titer: Median and 25th/75th quantiles (min, max) of the ADA titer for peak ADA titer of treatment induced ADA positive patients
 - Last ADA titer (final assessment): Median and 25th/75th quantiles (min, max) of the ADA titer of treatment induced ADA positive patients
- Number (%) of patients with positive neutralizing antibody (NAb)

- NAb inhibition of catalytic activity
- NAb inhibition of cellular uptake

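### SAP 2.6.11 leaves out three immunogenicity outputs planned in protocol 11.4.2.8 without declaring it, and its evaluable rule admits patients who cannot enter the numerator of two ADA rates

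*Protocol*

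**What the plan says.** Protocol 9.1 counts immune response assessments among the primary safety endpoints. Protocol 11.4.2.8 then sets out the IgG summaries: "Percentage of patients who seroconverted to olipudase alfa, time to seroconversion and peak IgG antibody titer will be summarized using descriptive statistics". It adds: "IgG antibody titer values will be summarized using descriptive statistics at each study visit". The same section names circulating immune complex among the results to be listed by patient.

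SAP 2.6.11 opens its output list with "The following information will be provided by age group cohorts and overall". The list gives baseline status, treatment-boosted and treatment-induced counts, transient, persistent and indeterminate classes with sub-classes of the persistent one, and neutralizing antibody counts. It has two titer summaries. One is "Peak ADA titer: Median and 25th/75th quantiles (min, max) of the ADA titer for peak ADA titer of treatment induced ADA positive patients". The other gives the same statistics for each patient's final titer, again only in the treatment-induced group.

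Its data-listing sentence covers IgG, neutralizing antibody, IgE, tryptase, complement and skin tests.

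Two definitions in the same section drive the rates. The first is "A patient with at least one anti-drug antibody (ADA) response available in the database is considered evaluable". The second is "A patient whose ADA status is positive anytime post-baseline and is negative or missing at baseline is considered to have treatment-induced ADA". The evaluable count is the divisor both for ADA incidence (boosted plus induced) and for the pre-existing ADA rate.

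SAP 1.5 lists the departures from the protocol's statistical section. There are three: the baseline for white cells, platelets and hemoglobin; the listing of acute phase reactions and cytokine release syndrome; and the removal of the post-treatment period.

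**The concern.** Two planned summaries and one planned listing of a primary-endpoint component are missing from the SAP, and a reader of SAP 1.5 would not learn of it. Without time to seroconversion, no table shows when antibodies first appear. Without titer by visit, no table shows the titer level at any fixed time, and treatment-boosted patients get no titer summary at all. Other serial safety measures do not have this gap: the SAP summarizes laboratory values, vital signs, ECG and safety biomarkers by time point.

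The second issue is narrower. A rate should be divided by the patients in whom the event could have been observed. A patient with only a baseline sample cannot become induced or boosted, yet is in the incidence denominator. A patient with no baseline sample cannot be shown to have pre-existing antibody, yet is in that denominator.

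**Working it through.** **1. Protocol 11.4.2.8 against SAP 2.6.11**

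| Planned in the protocol | In the SAP |
|---|---|
| Percentage seroconverted | Present in substance, as treatment-induced ADA |
| Time to seroconversion | Absent |
| Peak IgG titer | Present, but limited to treatment-induced patients |
| IgG titer at each visit | Absent; last titer is given, treatment-induced patients only |
| By-patient IgG listing | Present |
| By-patient circulating immune complex listing | Absent from the listing sentence, although the section says samples will be taken for it |

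**2. Is the change declared or covered elsewhere?** None of the three items in SAP 1.5 concerns immunogenicity. SAP 1.6 has two blacked-out bullets, but that section records changes from SAP Version 2, not from the protocol. SAP 2.3.2 says in general terms that baseline safety data, which include immune response, will be shown with later values. It specifies no titer statistics by visit.

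**3. How many samples are involved?** The flow chart in protocol 1.2 gives the IgG schedule: "Every 2 weeks from Day 1 through Wk16, then at quarterly visits (Wk26, Wk38, Wk52) and Wk 64". Weeks 0 to 16 in steps of 2 give 16/2 + 1 = 9 samples. Weeks 26, 38, 52 and 64 add 4, so 9 + 4 = 13, of which 12 are post-baseline. This agrees with the 13 antibody samples in each of Tables 4 to 6 of protocol 9.5. Descriptive titer statistics at up to 13 visits therefore become two titer summaries, peak and last.

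**4. Effect of the evaluable rule.** The plan states no ADA rate, so there is no figure to reproduce. N = 20 is the planned minimum enrolment (protocol 11.1). All counts below are assumptions.

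Incidence as the SAP defines it is 100·x/N. With the k baseline-only patients removed it is 100·x/(N − k).

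| Positives x, N = 20 | SAP rule | k = 1 | k = 2 | k = 3 |
|---|---|---|---|---|
| 5 | 25.0% | 26.3% | 27.8% | 29.4% |
| 10 | 50.0% | 52.6% | 55.6% | 58.8% |
| 15 | 75.0% | 78.9% | 83.3% | 88.2% |

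For x = 10 and k = 1: 10/19 = 52.6% against 10/20 = 50.0%, a difference of 2.6 points.

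The rates are also reported by age cohort. The infant/early child cohort has a planned minimum of 2 + 2 = 4 patients. With 2 positives and one baseline-only patient, 2/3 = 66.7% becomes 2/4 = 50.0%.

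The pre-existing rate behaves the same way, with m patients lacking a baseline sample: 100·p/N against 100·p/(N − m). For an assumed p = 2 and m = 1, 2/20 = 10.0% against 2/19 = 10.5%.

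**The case against.** The strongest reply is that the SAP still uses the serial samples. Boosted status depends on a titer ratio of at least 4 at any post-baseline visit. The duration classes use the interval between first and last positive samples, with a 16-week cut, and the status of the last sample. By-patient IgG listings remain, and with about 20 patients the first positive visit can be read from them. This stands. A reader might infer that the report could not describe how antibodies evolve, or could not tell whether they arise before or after the target dose; the documents do not support that. What is lost is tabulation, and the protocol promised summaries as well as listings.

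A reader might also infer that IgG is drawn every 2 weeks to Week 16 in order to place antibody onset on the dose escalation. The protocol gives no such purpose, so the point does not rest on it.

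On the denominators, the reply is that the cases should be few. Safety analyses include only infused patients, a pre-infusion sample is scheduled for everyone on Day 1, the next is due at Week 2, and withdrawal evaluations are requested. That limits the size, not the logic.

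Finally, a reader might take the treatment-induced label for positives with a missing baseline to be an error that inflates incidence. It is an explicit choice, conservative for a safety endpoint, and in line with SAP 2.11.2, which treats adverse events of uncertain onset as treatment-emergent and missing relationship as possibly related. It should stand.

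Circulating immune complex is tested only after certain infusion reactions, so that omission is minor.

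**Conclusion.** The point holds as a reconcile-or-declare item. Time to seroconversion, IgG titer by visit and the circulating immune complex listing are planned in the protocol, absent from SAP 2.6.11, and not declared in SAP 1.5. The consequence is that onset timing and by-visit titers for part of the primary endpoint would not be tabulated. The data are collected, and the IgG results are listed.

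The evaluable rule gives the wrong denominator for two rates. Its effect is small overall: 2.6 points for one baseline-only patient among 20 under the assumed 10 positives. It can be visible in a small cohort: 16.7 points (66.7 − 50.0) in a cohort of 4 under the assumed 2 positives. These sizes depend wholly on assumed counts, in descriptive percentages that are not tested. No conclusion is drawn about the direction or size of any error in the actual results.

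**What to change.** In SAP 2.6.11:

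- Add time to first positive IgG in treatment-induced patients.
- Add descriptive statistics of IgG titer by scheduled visit, by age cohort and overall.
- Add circulating immune complex to the listing sentence.
- Divide ADA incidence by the number of patients with one or more post-baseline ADA results.
- Divide the pre-existing ADA rate by the number of patients with a baseline ADA result.
- Keep the rule for positives with a missing baseline. A footnote giving their number is optional.

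If the sponsor prefers not to restore the first three items, SAP 1.5 should declare and justify their removal.

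The cost is two standard tables and some SAP wording. No new data are needed.

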#### **11.4.3 Pharmacokinetic analyses**

Plasma concentration-time data will be analyzed by non-compartmental methods, nonlinear mixed effects modeling or by population-based analysis, based upon patient age and data suitability. Values will be reported for individual subjects and summarized using descriptive statistics by dose level and study week as appropriate. These will use the pharmacokinetic population.

#### **11.4.4 Pharmacodynamic analyses**

Pharmacodynamic endpoints are defined in [Section 9.2.3](#).

Concentration-time data for sphingomyelin and metabolite levels (eg, ceramide, lyso-sphingomyelin) will be summarized using descriptive statistics. If appropriate, the following parameters will also be assessed:  $C_{max}$ ,  $T_{max}$ , and area under the effect-time curve. Individual and descriptive statistics will be presented.

Pharmacodynamic parameters will be summarized using descriptive statistics using the pharmacodynamics population. Change from baseline will be calculated and summarized.

Exploratory correlation analyses will be attempted to evaluate relationships between different pharmacodynamic markers and between sphingomyelin levels from different sources.

These analyses will be conducted by age cohort – in overall population as well as by manufacturing scale, as appropriate.

#### **11.4.5 Exploratory efficacy analyses**

Efficacy assessments are described in [Section 9.2.2](#).

Efficacy analyses will be performed on the modified intent-to-treat analysis set. For each exploratory efficacy assessment, observed measures, change from baseline and/or percent change from baseline to week 52 or 64, as appropriate, will be listed and summarized using descriptive statistics overall and separately by timepoint and age cohort, including 95% confidence intervals.

Categorical variables (eg, pulmonary imaging, chest X-ray) will be summarized using frequencies and percentages according to time points collected from screening or baseline to Week 52 (or last study assessment).

The same efficacy analyses will also be performed by manufacturing scale.

#### **11.4.6 Pharmacokinetic-pharmacodynamic analyses**

Exploratory PK-PD analyses may be performed to elucidate exposure-response relationships with biomarkers of safety and/or efficacy. The PK-PD relationships may be explored graphically. If a relationship is apparent, PK-PD modeling may be attempted and results reported, as appropriate.

### **11.5 INTERIM ANALYSIS**

Analysis of data, including summary tables, figures and listings, may be conducted intermittently during the study and upon completion of a cohort's key milestones, eg, week 26 or 52 efficacy assessments.

## 12 ETHICAL AND REGULATORY CONSIDERATIONS

### 12.1 ETHICAL AND REGULATORY STANDARDS

This clinical trial will be conducted by the sponsor, the investigator, delegated investigator staff and subinvestigator, in accordance with the principles laid down by the 18th World Medical Assembly (Helsinki, 1964) and all applicable amendments laid down by the World Medical Assemblies, and the ICH guidelines for good clinical practice (GCP), all applicable laws, rules and regulations.

This clinical trial will be recorded in free, publicly accessible, internet-based registries, no later than 21 days after the first patient enrollment, in compliance with applicable regulatory requirements and with Sanofi public disclosure commitments.

### 12.2 INFORMED CONSENT

The investigator (according to applicable regulatory requirements), or a person designated by the investigator, and under the investigator's responsibility, should fully inform the patient (and the parent[s] or guardian[s]) of all pertinent aspects of the clinical trial including the written information given approval/favorable opinion by the ethics committee (IRB/IEC). All participants should be informed to the fullest extent possible about the study in language and terms they are able to understand.

Prior to a patient's participation in the clinical trial, the written informed consent form should be signed, name filled in and personally dated by the patient or by the patient's parents or by the patient's legally acceptable representative, and by the person who conducted the informed consent discussion. If only 1 one parent or guardian signs the consent form, the investigator must document the reason why only 1 parent or guardian's signature. A copy of the signed and dated written informed consent form will be provided to the patient.

Participants who can read the assent form will do so before writing their name and dating or signing and dating the form.

Participants who can write but cannot read will have the assent form read to them before writing their name on the form.

Participants who can understand but who can neither write nor read will have the assent form read to them in the presence of an impartial witness, who will sign and date the assent form to confirm that assent was given.

The informed consent form used by the investigator for obtaining the patient's informed consent must be reviewed and approved by the sponsor prior to submission to the appropriate Ethics Committee (IRB/IEC) for approval/favorable opinion.

In relation with the population of patients exposed in the trial ie, pediatric/minor patients, the IRB/IEC should ensure proper advice from specialist with pediatrics expertise (competent in the area of clinical, ethical and psychosocial problems in the field of pediatrics) according to national regulations. This should be documented.

### **12.3 INSTITUTIONAL REVIEW BOARD/INDEPENDENT ETHICS COMMITTEE (IRB/IEC)**

As required by local regulation, the investigator or the sponsor must submit this clinical trial protocol to the appropriate IRB/IEC, and is required to forward to the respective other party a copy of the written and dated approval/favorable opinion signed by the Chairman with IRB/IEC composition.

The clinical trial (study number, clinical trial protocol title and version number), the documents reviewed (clinical trial protocol, informed consent form, Investigator's Brochure, investigator's curriculum vitae [CV], etc) and the date of the review should be clearly stated on the written (IRB/IEC) approval/favorable opinion.

IMP will not be released at the study site and the investigator will not start the study before the written and dated approval/favorable opinion is received by the investigator and the sponsor.

During the clinical trial, any amendment or modification to the clinical trial protocol should be submitted to the IRB/IEC before implementation, unless the change is necessary to eliminate an immediate hazard to the patients, in which case the IRB/IEC should be informed as soon as possible. It should also be informed of any event likely to affect the safety of patients or the continued conduct of the clinical trial, in particular any change in safety. All updates to the investigator's Brochure will be sent to the IRB/IEC.

A progress report is sent to the IRB/IEC at least annually and a summary of the clinical trial's outcome at the end of the clinical trial.

